#### 6.2.1.1.3.1. Main Analysis

Estimand strategy: treatment policy and composite (section 2.2.2.1).

- Analysis set: mITT-infected (section 4). Participants must have no LRTI at randomization.
- Analysis methodology: Proportion of participants will be summarized (section 5.2).
- Intercurrent events and missing data: The intercurrent events "discontinuation from or non-compliance to the planned course of treatment," "discontinuation from the study," and "initiation of rescue or other concomitant medications" are addressed by including all available data in the analysis regardless of discontinuation, non-compliance, or use of concomitant medications. The composite strategy is followed for the intercurrent event of "death" by incorporating death into the endpoint, ie, death will be considered development of LRTI. The intercurrent event of "RSV-related hospitalization" after first dose of study medication will also be considered development of LRTI.
- Results will be presented similarly to those for the primary endpoint (section 6.1.1.1).

## 6.2.1.1.4. Resolution of LRTI at Day 15

#### 6.2.1.1.4.1. Main Analysis

- Estimand strategy: treatment policy and composite (section 2.2.2.1).
- Analysis set: mITT-infected (section 4). Participants must have either nsLRTI or sLRTI at randomization.
- Analysis methodology: Proportion of participants will be summarized (section 5.2).
- Intercurrent events and missing data: The intercurrent events "discontinuation from or non-compliance to the planned course of treatment," "discontinuation from the study," and "initiation of rescue or other concomitant medications" are addressed by including all available data in the analysis regardless of discontinuation, non-compliance, or use of concomitant medications. The composite strategy is followed for the intercurrent event of "death" by incorporating death into the endpoint, ie, death will be considered "not resolved". The intercurrent event of "RSV-related hospitalization" after first dose of study medication will also be considered as LRTI "not resolved".
- Results will be presented similarly to those for the primary endpoint (section 6.1.1.1).

# 6.2.1.1.5. Days Alive and Free from Hospital Stay (Hospital-Free Days) through Day 28 6.2.1.1.5.1. Main Analysis

- Estimand strategy: treatment policy and composite (section 2.2.2.1).
- Analysis set: mITT-infected (section 4).
- Analysis methodology: Mean number of hospital-free days through Day 28 will be summarized (section 5.2).
- Intercurrent events and missing data: The intercurrent events "discontinuation from or non-compliance to the planned course of treatment," "discontinuation from the study," and "initiation of rescue or other concomitant medications" are addressed by including all

available data in the analysis regardless of discontinuation, non-compliance, or use of concomitant medications. The composite strategy is followed for the intercurrent event of "death" by incorporating death directly into the endpoint. No imputation for missing data will be performed for participants who discontinue prior to the Day 28 visit; if on the date of discontinuation, the participant is not hospitalized, the remainder of the time until Day 28 will be assumed to be hospital-free.

 The sample size, mean, SD, median, and range for observed number of hospital-free days will be presented by treatment group.

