8.2. Efficacy Assessments

8.2.1. RSV-related hospitalizations and Medical Details

Details of participants' RSV-related medical visits (ie, hospitalization of any duration, urgent care, emergency room) will be collected during study visits, including level of care (ICU status), dates of utilization (including admission and discharge), and discharge status, as applicable.

For the primary endpoint, hospitalization of at least 24 hours of acute care is defined as ≥ 24 hours of acute care in a hospital or similar acute care facility. This includes specialized acute medical care unit within an assisted living facility or nursing home. Participants who are waiting in an emergency department or other hospital unit for an inpatient bed to become available are considered hospitalized provided that a decision to admit to inpatient care has occurred. For the secondary endpoint of RSV-related visits (urgent care/ED/hospital) or death from any cause, no minimum duration of hospitalization is required.

Investigators will determine if a medical visit is related to RSV. For reference, RSV related medical visits are those attendances that would not otherwise occur in the absence of the RSV infection. These may include visits for: deterioration or decompensation of the lung function that require supplemental oxygen; development of secondary respiratory tract infections that require antibiotic treatment; management of severe symptoms associated with RSV such as fever; worsening or decompensation of cardiac or renal function in patients with underlying cardiac or renal disease.

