8.2.2. Survival status

Information about the death of a participant may be collected from death registries, hospital databases, other healthcare professionals, from participant's legal representatives, or other persons authorized by the participant and according to local regulations. The death of a participant cannot be assumed by their non-responsiveness, as the participant may be lost to follow-up.

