#### 5. GENERAL METHODOLOGY AND CONVENTIONS

## 5.1. Hypotheses and Decision Rules

The study was discontinued, with very few participants enrolled. No inferential testing will be performed.

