#### 6.2.1.2. Other Efficacy-Related Secondary Endpoints

Proportion of participants with progression of LRTI through Day 3, 5, 15, and 28

These endpoints will be summarized with the same methods as the similar endpoint through Day 10 (section 6.2.1.1.2.1).

Proportion of participants with development of LRTI through Day 3, 5, 15, and 28

These endpoints will be summarized with the same methods as the similar endpoint through Day 10 (section 6.2.1.1.3.1).

Proportion of participants with resolution of LRTI at Day 3, 5, 10, and 28

These endpoints will be summarized with the same methods as the similar endpoint at Day 15 (section 6.2.1.1.4.1).

Proportion of participants with improvement in LRTI status at Day 3, 5, 10, 15, and 28

These endpoints will be summarized with the same methods as the endpoint of resolution of LRTI at Day 15 (section 6.2.1.1.4.1).

Number of RSV related days in hospital through Day 28.

Health resource utilization data will be summarized by treatment group. This will include number of days of RSV related hospital stay through Day 28. The analyses will be done using the mITT-infected population. Descriptive statistics (ie, mean, SD, median, range) will be used to summarize this endpoint. No imputation for missing data will be performed for participants who discontinue or die prior to the Day 28 visit; the count of RSV related hospital days will be truncated at the date of discontinuation or death.

Number of RSV related days in ICU through Day 28.

Health resource utilization data will be summarized by treatment group. This will include number of days of RSV related ICU stay through Day 28. The analyses will be done using the mITT-infected population. Descriptive statistics (ie, mean, SD, median, range) will be used to summarize this endpoint. No imputation for missing data will be performed for participants who discontinue or die prior to the Day 28 visit; the count of RSV related ICU days will be truncated at the date of discontinuation or death.

 Proportion of participants with a clinical response of Improvement or Resolution at Day 5, 10, 15, and 28.

These endpoints will be summarized with the same methods as the endpoint of resolution of LRTI at Day 15 (section 6.2.1.1.4.1). The analysis set is the mITT-infected analysis set (section 4).

 Proportion of participants with undetectable RSV viral load at each study visit through Day 28.

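### Does SAP 6.2.1.1.5.1 present imputed hospital-free days as observed and leave participants who discontinue in hospital without a rule?

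*SAP*

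**What the plan says.** Hospital-free days through Day 28 is the fifth key secondary endpoint. SAP 3.2.1.1 counts every hospital day, whether or not it is related to RSV. SAP 6.2.1.1.5.1 sets three rules for it:

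- Death is handled by "incorporating death directly into the endpoint", and all available data are used regardless of discontinuation.
- For early leavers, "No imputation for missing data will be performed for participants who discontinue prior to the Day 28 visit"; in the same sentence, if the participant is not in hospital on that date, "the remainder of the time until Day 28 will be assumed to be hospital-free".
- The sample size, mean, SD, median and range of the "observed number of hospital-free days will be presented by treatment group".

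For the neighboring endpoint of RSV-related hospital days, SAP 6.2.1.2 also says there is no imputation, and adds that "the count of RSV related hospital days will be truncated at the date of discontinuation or death".

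SAP Appendix 2.2 refers further endpoint derivations to an Analysis and Reporting plan, which is not among the documents. SAP 5.1 states: "No inferential testing will be performed".

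**The concern.** Treating unseen days as hospital-free is a deterministic single imputation, and a favorable one. A sentence that first says nothing is imputed and then fills the days appears to contradict itself, and calling the result observed adds to that. A reader of the abbreviated study report might not realize that some counted days were never followed.

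Three further points look like gaps.

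- The fill applies only to leavers who are out of hospital. Neither the SAP nor the protocol has a sentence for someone who leaves the study during a stay.
- Protocol 8.2.1 says hospital details "will be collected during study visits, including level of care (ICU status), dates of utilization (including admission and discharge), and discharge status", so a discharge after the participant has left may go unrecorded.
- Protocol 8.2.2 says "Information about the death of a participant may be collected from death registries, hospital databases, other healthcare professionals", so a death may become known after discontinuation, and the fill sentence does not mention that case.

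With very few participants enrolled, one person counted differently could visibly move an arm mean. SAP 6.2.1.2 also attaches the same no-imputation wording to truncation, which at first sight means the reverse.

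**Working it through.** The documents give no arm sizes, numbers of leavers or later hospitalization rates for the stopped study, and no figure of their own to reproduce. Every participant-level input below is an assumption. Only the 28-day horizon comes from the SAP.

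**1. How many days the fill supplies.** Filled days = 28 − day of leaving.
- Leaves well on Day 5: 28 − 5 = 23.
- Leaves well on Day 20: 28 − 20 = 8.

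With no earlier stay, both score 28. The fill is real, so the literal wording is wrong for these people.

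**2. How far the fill can bias the mean.** Expected overstatement = share leaving × share of those later hospitalized unseen × length of stay.
- Low: 0.05 × 0.05 × 5 = 0.0125 days.
- High: 0.10 × 0.15 × 8 = 0.12 days, and 0.12 / 28 = 0.43%.

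**3. Does the SAP use one phrase in two opposite senses?** Section 6.2.1.2 truncates a count of hospital days, so nothing is added after the participant leaves. Section 6.2.1.1.5.1 counts the complement, days free of hospital. For a leaver who is well, it too adds no hospital days after that date. Take a survivor who leaves on Day 5 without any stay: truncated hospital days = 0, and hospital-free days = 28 − 0 = 28, the SAP's own value. The two rules make the same assumption for these leavers.

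An arm of 20 shows the same thing. Suppose 3 leave well on Day 5, 2 completers have 7-day stays, and 15 completers have none.
- SAP rule: (18 × 28 + 2 × 21) / 20 = 546 / 20 = 27.3.
- The 17 completers only: (15 × 28 + 2 × 21) / 17 = 462 / 17 = 27.18.
- Stopping the free-day count at Day 5: (15 × 28 + 2 × 21 + 3 × 5) / 20 = 477 / 20 = 23.85.

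The last figure scores each unseen day as if the participant were in hospital or dead. Section 6.2.1.2 does not do that, so 23.85 is not a competing reading of the SAP. The example is also harsh: 3 / 20 = 15% leave, above the 5-10% assumed in step 2.

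**4. The leaver who is in hospital.** Suppose admission on Day 3 and leaving the study, still in hospital, on Day 5. Days 1 and 2 are free, which gives 2. If Days 6 to 28 were all counted as free, the value would be 2 + 23 = 25. That difference of 23 days would move an arm mean by 23 / 10 = 2.3, 23 / 20 = 1.15 or 23 / 40 = 0.575 days in arms of 10, 20 or 40.

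The upper value does not survive a reading of the text. The fill is conditional on not being hospitalized, and a programmer who filled hospitalized leavers in the same way would make that condition pointless. If a discharge date is on record, the all-available-data rule supports using it. Dropping the participant would conflict with that rule and with the mITT-infected set. Without a discharge date, the natural value is 2.

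**5. Death.** The endpoint is days alive and free from hospital, and death is composite. The fill assumes freedom from hospital and says nothing about survival. A known death therefore ends the count under the rules as written.

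**6. Capture of hospital dates.** Protocol 8.2.1 describes RSV-related visits, whereas this endpoint counts all hospital days. That section therefore does not show how discharge dates for this endpoint are recorded or lost.

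**The case for a change.** The strongest case for acting is that the words are wrong on their face and cheap to correct. Filling days is imputation, and a count containing filled days is not observed. Protocol 9.3.1 places imputation rules in the SAP, so pointing to another plan is not a complete answer for the hospitalized leaver. In a very small study, one undefined participant matters more than in the planned trial of about 2375.

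Part of this stands. The labels are loose, and no explicit sentence covers a leaver in hospital. Context explains the wording without fully excusing it. SAP version 2 removed multiple imputation and inferential analyses, and Protocol 9.3.3 had planned a model with symptom duration as a covariate for this endpoint. In that setting, no imputation most plausibly means no statistical imputation, and observed means not model-based. The SAP does not say so.

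The argument fails on consequence. Correcting the labels would leave every reported value the same, because the fill itself would stay. The hospitalized leaver has a sensible reading from the condition and the available-data rule, and nothing in the documents shows that such a participant exists. Adding counts of filled days beside the mean is a reporting preference: SAP 6.6.2 already tabulates completions, discontinuations and their reasons by arm.

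**Conclusion.** The textual observation is correct, but no change follows. The no-imputation and observed labels are a slip of wording, and the rule actually applied is plain from the same sentence. The case of leaving while in hospital is a detail that an analyst would settle from the conditional wording and any recorded discharge, and the Analysis and Reporting plan may already settle it. Death is covered by the composite definition, and for well leavers the neighboring truncation rule agrees with this one.

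The expected overstatement from the fill is 0.0125 to 0.12 of 28 days, under 0.5%. That rests on assumed rates of 5-10% leaving, 5-15% of those later hospitalized unseen, and 5-8 day stays. The larger shifts of 2.3, 1.15 and 0.575 days require a reading of the hospitalized leaver that the text points away from. No test, interval or error rate is involved: the study was discontinued for business reasons with very few participants, and the SAP provides descriptive summaries only. This conclusion would be weaker if the endpoint still carried a formal comparison, or if several participants were known to have left during a hospital stay with no discharge date recorded.

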#### 6.2.1.2. Other Efficacy-Related Secondary Endpoints

Proportion of participants with progression of LRTI through Day 3, 5, 15, and 28

These endpoints will be summarized with the same methods as the similar endpoint through Day 10 (section 6.2.1.1.2.1).

Proportion of participants with development of LRTI through Day 3, 5, 15, and 28

These endpoints will be summarized with the same methods as the similar endpoint through Day 10 (section 6.2.1.1.3.1).

Proportion of participants with resolution of LRTI at Day 3, 5, 10, and 28

These endpoints will be summarized with the same methods as the similar endpoint at Day 15 (section 6.2.1.1.4.1).

Proportion of participants with improvement in LRTI status at Day 3, 5, 10, 15, and 28

These endpoints will be summarized with the same methods as the endpoint of resolution of LRTI at Day 15 (section 6.2.1.1.4.1).

Number of RSV related days in hospital through Day 28.

Health resource utilization data will be summarized by treatment group. This will include number of days of RSV related hospital stay through Day 28. The analyses will be done using the mITT-infected population. Descriptive statistics (ie, mean, SD, median, range) will be used to summarize this endpoint. No imputation for missing data will be performed for participants who discontinue or die prior to the Day 28 visit; the count of RSV related hospital days will be truncated at the date of discontinuation or death.

Number of RSV related days in ICU through Day 28.

Health resource utilization data will be summarized by treatment group. This will include number of days of RSV related ICU stay through Day 28. The analyses will be done using the mITT-infected population. Descriptive statistics (ie, mean, SD, median, range) will be used to summarize this endpoint. No imputation for missing data will be performed for participants who discontinue or die prior to the Day 28 visit; the count of RSV related ICU days will be truncated at the date of discontinuation or death.

 Proportion of participants with a clinical response of Improvement or Resolution at Day 5, 10, 15, and 28.

These endpoints will be summarized with the same methods as the endpoint of resolution of LRTI at Day 15 (section 6.2.1.1.4.1). The analysis set is the mITT-infected analysis set (section 4).

 Proportion of participants with undetectable RSV viral load at each study visit through Day 28.

This endpoint will be summarized at each study visit (Section 5.2). No imputation for missing data will be performed. The summary will be done using the mITT-infected population.

Change from baseline in RSV viral load at each study visit through Day 28.

Participants are excluded from the analysis for reasons of Not Detected, Zero or Missing baseline viral load result, and local (nonvalidated) swabs use. Results from samples collected at non-nasopharyngeal site (like nostril, other or missing) are also excluded, as well as exclusions due to non-validated swab use (only viral load data based on samples collected through validated swab will be used for analyses).

The viral load measured in nasopharyngeal samples over time will be evaluated. The absolute viral load and change from baseline to each visit (Day 3, Day 5, Day 10, Day 15, Day 28) in viral load will be summarized by treatment group with descriptive statistics (n, mean, SD, median, minimum, and maximum). A spaghetti plot of viral load values over time (by visit) will also be produced, differentiating participants from each treatment group. The analyses will be done using the mITT-infected population.

#### 6.2.2. Safety-Related Secondary Endpoints

- Proportion of participants with TEAEs through Day 35.
- Proportion of participants with SAEs through Day 35.

All adverse events will be coded according to MedDRA. The incidence of TEAEs and SAEs (if any) will be summarized by treatment group, SOC, and PT for the safety analysis set.

#### 6.2.3. Pharmacokinetic Secondary Endpoints

Plasma concentrations of sisunatovir at steady state (Day 3 or later)

The plasma concentrations of sisunatovir will be listed and descriptively summarized by specific PK sampling windows or nominal sampling time as appropriate.

#### 6.3. Other Safety Summaries and Analyses Endpoint(s)

All safety analyses will be performed on the safety population.

Standard summary tables and listings will be generated in accordance with Clinical Data Interchange Standards Consortium (CDISC) and Pfizer Standards (CaPS) for safety reporting for the following parameters: adverse events, lab parameters, vital signs, discontinuations from study, discontinuations from treatment, and treatment duration.

#### 6.3.1. Adverse Event Data

The intensity of TEAEs will be summarized by treatment group, SOC, and PT for the safety analysis set.

#### 6.3.2. Laboratory Data

All laboratory data will be reported in accordance with Clinical Data Interchange Standards Consortium (CDISC) and Pfizer Standards (CaPS) for safety reporting.

## 6.3.3. Vital Signs Data

All vital sign data will be descriptively summarized by treatment group within the safety analysis set and reported in accordance with the Pfizer Data Standards for safety reporting.

## 6.4. Tertiary/Exploratory Endpoints

No tertiary/exploratory endpoints will be summarized for the abbreviated CSR.

## 6.5. Subset Analyses

No subset analyses will be performed for the abbreviated CSR.

#### 6.6. Baseline and Other Summaries and Analyses

#### 6.6.1. Baseline Summaries

Baseline demographic and other characteristics will be tabulated for the FAS and summarized by treatment group. This will include age, sex, race, ethnicity, weight, height, BMI, geographic region, presence/absence of specific risk factors, and number of risk factors.

The levels of geographic region will be as follows:

All baseline disease characteristics will be summarized by treatment group for the FAS. This will include symptom duration, number of days since diagnosis (start date of study treatment – date of diagnosis + 1 [if participant is randomized but not treated, randomization date will be used in place of start date of study treatment]), presence/absence of individual signs/symptoms (from the Signs and Symptoms of ARI CRF), and LRTI status (from the LRTI Assessment Details CRF; any LRTI [yes/no]; if yes, intensity grading

[mild/moderate/severe]; meet criteria for Severe LRTI? [yes/no]; RSV-related? [yes/no/unknown]).

Symptom duration is calculated as [6]

For viral load data, baseline visit is set up according to study days of Day -2 to Day 1. Only post-dose results that are within 1 hour post start of dosing will be treated as Baseline data.

#### 6.6.2. Study Conduct and Participant Disposition

The number of participants screened, randomized to the double blind treatment phase..., and treated...will be summarized from the FAS. The number of participants completing and discontinuing by study phase, as well as the number of participants in each analysis set will be summarized by treatment group. The reason for all discontinuations will be summarized by treatment group.

### 6.6.3. Study Treatment Exposure

Duration of treatment will be summarized within the safety analysis set.

The duration of treatment will be calculated as follows:

date of last dose of study drug - date of first dose of study drug +1.

#### 7. INTERIM ANALYSES

#### 7.1. Introduction

The study was discontinued, with very few subjects enrolled, prior to any planned IAs.

#### 7.2. Interim Analyses and Summaries

Not applicable.

#### 8. REFERENCES

Not applicable.

